- Multiple studies have shown that suppressing the expression of EWS-FLI1 effectively limits the tumorigenicity of ESFT cells. Laboratory studies have shown that mithramycin effectively suppresses the activity of EWS-FLI1 both *in vitro* and *in vivo*.

Objectives (primary):

- Phase I portion of this study is to: determine the tolerability, toxicity, and the recommended phase II dose of mithramycin in children and adolescents with refractory extracranial solid tumors.
- Phase II portion of this trial is to: determine the objective response rate (CR and PR) of Ewing sarcoma to mithramycin in children and adults using RECIST criteria when administered at 17.5 microgram/kg over 6 hours once daily for 7 days to be repeated every 28 days until unacceptable toxicity or disease progression.
- Phase II portion of this trial to: evaluate if mithramycin inhibits NR0B1 in tumor tissue and determine changes in gene expression signature pre-treatment and at steady state on day +4 of treatment in patients \geq 18 years old with Ewing sarcoma and EWS/FLI1 fusion transcript with disease amenable to percutaneous biopsy.

Eligibility:

- Phase I Portion: children (\geq 12 months) and adolescents (\leq 17 years) with recurrent or refractory extracranial solid tumors.
- Phase II Portion in adults: adults (\geq 18 years of age at enrollment) with recurrent or refractory measurable extracranial Ewing sarcoma and the EWS-FLI1 fusion transcript.
- Phase II Portion in children and adolescents: Once the adult dose is deemed safe, children (\geq 12 months) and adolescents (\leq 17 years) with recurrent or refractory measurable extracranial Ewing sarcoma and the EWS-FLI1 fusion transcript will begin enrollment to the Phase II portion.
- Participants must meet safety laboratory criteria and prior therapy limitations.

Design:

- Phase I Portion: Mithramycin will be administered in escalating doses to children and adolescents intravenously over 6 hours once daily for 7 days to be repeated every 28 days until unacceptable toxicity or disease progression. Mithramycin will be given with

dexamethasone prophylaxis to ameliorate hepatotoxicity. The cohort at the recommended dose or MTD will be expanded up to 12 patients, and attempts will be made to enroll 6 patients that are ≥ 12 years of age and 6 patients that are < 12 years of age to gain experience with a broad age range of patients. A maximum of 18 evaluable patients will be enrolled on the phase I portion.

- Phase II Portion: Using a Simon two stage design, mithramycin will be administered intravenously at 17.5 microgram/kg over 6 hours once daily for 7 days to be repeated every 28 days until unacceptable toxicity or disease progression to children and adults with Ewing sarcoma with EWS-FLI1 fusion transcript. Mithramycin will be given with dexamethasone prophylaxis to ameliorate hepatotoxicity. Up to 24 evaluable patients will be enrolled on the phase II portion.
- The Phase I and Phase II portions of the protocol will enroll patients simultaneously.

TABLE OF CONTENTS

Précis	3
TABLE OF CONTENTS	5
1 INTRODUCTION.....	10
1.1 Study Objectives	10
1.1.1 Primary Objectives.....	10
1.1.2 Secondary Objectives.....	10
1.2 Background and Rationale	10
1.2.1 Ewing Sarcoma Family of Tumors (ESFT)	10
1.2.2 Preclinical studies	12
1.2.3 Clinical studies in adults	13
1.2.4 Clinical activity.....	14
1.2.5 Clinical studies in children	15
1.2.6 Clinical Protocol 12C0135	15
1.3 Rationale summary	15
2 ELIGIBILITY ASSESSMENT AND ENROLLMENT	16
2.1 Eligibility Criteria	16
2.1.1 Inclusion Criteria	16
2.1.2 Exclusion Criteria	18
2.1.3 Recruitment Strategies	19
2.2 Screening Evaluation	19
2.2.1 General	19
2.2.2 Laboratory	19
2.2.3 Radiographic Evaluation.....	20
2.2.4 Cardiac Function Studies	20
2.2.5 Pathologic/Tissue Evaluation	20
2.3 Registration Procedures.....	20
2.3.1 Registration at NCI	21
3 STUDY IMPLEMENTATION.....	21
3.1 Study Design.....	21
3.1.1 Dose Limiting Toxicity	22
3.1.2 Dose Escalation in Phase I Portion	23

3.1.3	Phase II Portion.....	23
3.2	Drug Administration	24
3.3	Dose Reduction or Modifications	24
3.4	Criteria for Additional Cycles	25
3.5	On Study Protocol Evaluation (Appendix 3: Study Calendar).....	25
3.5.1	Monitoring During Active Treatment:.....	25
3.5.2	Monitoring after completion of treatment with mithramycin:	26
3.5.3	Off Study Evaluation (at least 30 days after last dose).....	26
3.6	Concurrent Therapies	26
3.7	Criteria for Removal from Protocol Therapy and Off Study Criteria.....	26
3.7.1	Criteria for removal from protocol therapy.....	26
3.7.2	Criteria for removal from Study	27
3.7.3	Off Study Procedure	27
4	CONCOMITANT MEDICATIONS AND SUPPORTIVE MEASURES	27
4.1	Management of Bleeding, Hematologic and Blood Product Support.....	27
4.2	Antiemetic Therapy.....	28
4.3	Hepatotoxicity Prophylaxis using dexamethasone	28
4.4	Antidiarrheals	28
4.5	Electrolyte Replacement	28
4.6	QTc Prolongation.....	28

1 INTRODUCTION

1.1 STUDY OBJECTIVES

1.1.1 Primary Objectives

- 1.1.1.1 Phase I portion of this study is to: determine the tolerability, toxicity, and recommended dose of mithramycin in children and adolescents with refractory extracranial solid tumors.
- 1.1.1.2 Phase II portion of this trial is to: determine the objective response rate (CR and PR) of Ewing sarcoma with EWS-FLI1 fusion transcript to mithramycin in children and adults using RECIST criteria when administered at 17.5 microgram/kg over 6 hours once daily for 7 days to be repeated every 28 days until unacceptable toxicity or disease progression. If the pediatric phase II dose of mithramycin differs from the adult phase II dose, the protocol will be amended to address accrual and response rate to mithramycin in children in a separate stratum.
- 1.1.1.3 Evaluate if mithramycin inhibits NR0B1 in tumor tissue, and determine changes in EWS/FLI1 gene expression signature by obtaining mandatory tumor biopsies pre treatment and at steady state on day +4 of treatment in patients \geq 18 years old with Ewing sarcoma and EWS/FLI1 fusion transcript and disease amenable to percutaneous biopsy (phase II).

1.1.2 Secondary Objectives

- 1.1.2.1 Describe pharmacokinetic parameters for each dose level using non-compartmental methods (phase I and II)
- 1.1.2.2 Evaluate NR0B1 expression in patients with Ewing sarcoma using immunohistochemistry on archival tumor tissue, if available (phase I and II)
- 1.1.2.3 To prospectively evaluate the feasibility and utility of volumetric analysis of target lesions, and descriptively compare volumetric measurements to 1D (RECIST), and 2D (WHO) measurements (phase I and II).
- 1.1.2.4 Define preliminarily time to progression (TTP) in patients with Ewing sarcoma (phase II)

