8.2.1 Methods of Analysis

Patients who are considered evaluable for response will be included in an analysis of time to progression. Time to progression will be estimated using the product-limit method of Kaplan and Meier. The probability of progression free survival at 6 months will be summarized. Response rates will be calculated as the percent of patients whose best response is a CR or PR, and the fraction of responses obtained will have a 95% confidence interval, which takes into consideration the two-stage nature of the design (50). Toxicity information recorded will include the type,

severity, time of onset, time of resolution, and the probable association with the study regimen. Tables will be constructed to summarize the observed incidence by severity and type of toxicity.

Time to progression will be taken as the number of days from enrollment until: (1) disease progression; (2) death because of treatment complications; (3) resection of measurable tumor; or (4) last patient follow-up whichever is first. Patients will be considered to have experienced a progression event if (1) or (2) occurs. Otherwise, the patient will be considered censored for time to progression.

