8.3 EVALUATION OF RESPONSE

Any patient who is enrolled and receives at least one dose of mithramycin will be considered evaluable for response provided: (1) the patient demonstrates progressive disease or death while on protocol therapy; (2) the patient is observed on protocol therapy for at least one cycle and the tumor is not removed surgically prior to the time complete response or partial response is confirmed; or (3) the patient demonstrates a complete or partial response as confirmed according to protocol criteria. Patients who electively terminate therapy before receiving all 7 doses of mithramycin during the first treatment cycle and do not expire within 28 days from start of treatment will be replaced. Patients who demonstrate a complete or partial response will be considered to have experienced a response. The evaluation period for determination of the best response will be 6 treatment cycles. All other patients will be considered non-responders.

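### Time to progression is analysed only in response-evaluable patients, so treated patients who stop event-free in cycle 1 are deleted instead of censored; the bias is probably small and has no fixed direction

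*Combined protocol and SAP*

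**What the plan says.** The objective in 1.1.2.4 is "Define preliminarily time to progression (TTP) in patients with Ewing sarcoma (phase II"; it carries no evaluability limit.

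Section 8.2.1 names the analysis set: "Patients who are considered evaluable for response will be included in an analysis of time to progression". The clock starts at entry: "Time to progression will be taken as the number of days from enrollment until" the first of progression, death from treatment complications, resection of measurable tumor, or last follow-up. Only the first two are events. For everyone else, "Otherwise, the patient will be considered censored for time to progression". The estimator is Kaplan-Meier, and a 6-month progression-free probability is to be reported.

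Section 8.3 makes a treated patient evaluable by one of three routes:
- "the patient demonstrates progressive disease or death while on protocol therapy";
- "the patient is observed on protocol therapy for at least one cycle", with no surgical removal of the tumor before a response is confirmed;
- "the patient demonstrates a complete or partial response as confirmed according to protocol criteria".

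It also replaces some patients: "Patients who electively terminate therapy before receiving all 7 doses of mithramycin during the first treatment cycle" who are still alive 28 days after starting treatment.

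Section 8.5 (Secondary Endpoints) does not mention time to progression. No all-treated set or sensitivity analysis is defined for it.

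**The concern.** Whether a patient belongs in the analysis is settled by what happens after the clock has started. A patient who progresses or dies on therapy in week 2 is kept as an event. A patient who stops permanently in week 2 without an event meets none of the three routes and is removed. Examples are the events in 3.3 that end treatment at once, and elective or administrative stops.

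That requirement has a purpose for a response rate, because response cannot be judged without some time on treatment. A Kaplan-Meier curve does not need it, because short follow-up is handled by censoring. Section 8.2.1 has the rule for these patients, and the evaluability filter keeps it from reaching them. The resection rule is affected in the same way: 8.2.1 censors at resection, but a patient resected before a confirmed response can be non-evaluable under 8.3.

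At stake is what the curve and the 6-month figure describe: the treated phase II patients named in the objective, or a subset chosen partly on outcome.

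**Working it through.** **The plan's own figures.** The documents give no sample size, median or dropout rate for time to progression. The evaluable denominator comes from the Simon design in 8.2 (stop if 0 of 9 respond; 3 or more of 24 to succeed). It reproduces: early termination at a 5% response rate is 0.95^9 = 0.630 (stated 63%), exact type I error is 0.093 and power at 25% is 0.903. It is not in dispute.

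**Who drops out.** Take a treated patient who stops for good on day 10, with no progression, death or confirmed response. Routes 1 and 3 fail for lack of an event or response, and route 2 fails because one cycle is 28 days. The patient is out of the set, although 8.2.1 would otherwise censor at last follow-up or count a later progression.

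**Size: assumptions, none of them in the documents.** Progression times are exponential with 20% progression-free at 6 months (182 days), so h = -ln(0.20)/182 = 0.00884 per day. A fraction q of 10%, 20% or 30% stops, uniformly over days 3-28. After stopping, the hazard is unchanged, doubled or tripled.

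- Fraction dropped (stopped while event-free): D = q × (e^(-3h) - e^(-28h))/(25h) = q × (0.9738 - 0.7807)/0.2211 = 0.874q.
- Evaluable-only 6-month figure: (1 - q) × 0.20/(1 - D). For q = 10%: 0.18/0.9126 = 19.7%. The hazard after stopping does not enter, because the stoppers have been removed.
- All-treated value, hazard unchanged: 20%.
- All-treated value, doubled: (1 - q) × 0.20 + q × 0.04 × 1.149, where 1.149 is the mean of e^(hC) over stopping days C.
- All-treated value, tripled: (1 - q) × 0.20 + q × 0.008 × 1.326, where 1.326 is the mean of e^(2hC).

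| Stop in cycle 1 | Dropped | Evaluable-only | True, unchanged | True, doubled | True, tripled |
|---|---|---|---|---|---|
| 10% | 8.7% | 19.7% | 20.0% | 18.5% | 18.1% |
| 20% | 17.5% | 19.4% | 20.0% | 16.9% | 16.2% |
| 30% | 26.2% | 19.0% | 20.0% | 15.4% | 14.3% |

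With stopping unrelated to prognosis, the evaluable-only figure is 0.3 to 1.0 points too low. With a raised hazard it is too high, from 1.3 points (10%, doubled) to 4.7 points (30%, tripled). A second model covers stoppers who do better: 2-month median, 10% stopping over days 0-28, stoppers at half the hazard. The true 6-month rate is 14.8% and the evaluable-only figure 12.4%, too low by 2.4 points.

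**What the remedy recovers.** Section 3.7.2 takes toxicity stoppers off study once toxicity resolves, at least 30 days after the last dose. Simulating the first model with stoppers kept in and censored 30 days after stopping gives:
- hazard unchanged, 10-30% stopping: 19.0-19.7% becomes about 20%, so the bias is removed;
- 10% stopping, doubled: 19.7% becomes 19.5%, true value 18.5%;
- 30% stopping, tripled: 19.0% becomes 17.5%, true value 14.3%.

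**Bounds without a model.** Add d dropped patients to 24 evaluable ones with a 20% rate. The all-treated rate lies between 0.20 × 24/(24 + d), if all of them progress before 6 months, and (0.20 × 24 + d)/(24 + d), if none do. That is 19.2-23.2% for d = 1, 18.5-26.2% for d = 2 and 17.1-31.4% for d = 4.

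**Precision.** At 20% with 24 patients the standard error is √(0.20 × 0.80/24) = 8.2 points.

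**The case against.** The case for leaving the text alone has real force.

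- **Few patients may be affected.** A reader might infer that every dose-limiting toxicity in cycle 1, hepatotoxicity above all, removes the patient. Section 3.3 does not support that: most such toxicities lead to a hold, with up to 42 days from the start of the cycle to recover and continuation at a reduced dose. Removal for non-recovery comes at day 42, after the 28-day cycle, so on a natural reading those patients count as observed for one cycle. What remains is the short list of immediate permanent stops in 3.3, plus elective and administrative stops. The documents do not support a 10-30% rate; that range is illustrative.
- **Follow-up is limited.** A reader might assume that the dropped patients are followed to progression. Section 3.7.2 takes toxicity stoppers off study when toxicity resolves, and anyone who enters another therapeutic study. The two-monthly imaging in Appendix 3 runs only until off study. Many later progressions would go unseen under any analysis set.
- **The downward bias may be overstated.** Disease is first imaged after cycle 2 (3.5.1.5), so cycle 1 progressions would be mainly clinical. A constant hazard from day 0 exaggerates the early failures that the set keeps.
- **Nothing turns on it.** The endpoint is secondary and described as preliminary, has no threshold, and does not enter the Simon decision.
- **Section 8.2.1 does not say that only evaluable patients enter.** True, but it names no other set, so an analyst following it would use this one.

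The first four limit the size and importance of the point. None restores the deleted patients.

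**Conclusion.** The point holds in a limited form. The set named in 8.2.1 is selected on events after enrollment, and it deletes treated patients whom the same section's censoring rule could handle. The objective gives no reason for that restriction.

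The effect is probably small: 0.3 to 1.0 points on a 20% 6-month figure if stopping is unrelated to prognosis, given the assumed exponential times and 10-30% stopping. The direction is not fixed. A reader might infer that the curve must look too good, or might take the 4.7-point gap as the expected error. The documents support neither: that gap needs both 30% stopping and a tripled hazard, and the sign reverses if stopping is unrelated to prognosis or if stoppers do better. Nor would the remedy recover the true all-treated value when stopping is informative, because the off-study rule limits what is observed. This is a cheap improvement to a descriptive secondary analysis; it does not affect the primary result.

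**What to change.** In 8.2.1, define the analysis set for time to progression and the 6-month probability as all phase II patients who received at least one dose at 17.5 mcg/kg. Keep the enrollment time origin and the stated event and censoring rules. Report the response-evaluable set as a sensitivity analysis, and leave the Simon denominator unchanged. This wording also settles whether the two patients treated at 25 mcg/kg enter this analysis, which 8.2 leaves open.

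Add that the report will give the number and timing of patients censored after a permanent stop in cycle 1, so a reader can judge how much rests on early, possibly informative, censoring.

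The cost is a sentence or two, with no extra patients. It needs no new data to remove the deletion bias. Removing the remaining bias from informative stopping would take follow-up for progression beyond what 3.7.2 provides.

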1.2 BACKGROUND AND RATIONALE

[figure not shown]
1.2.1 Ewing Sarcoma Family of Tumors (ESFT)

The Ewing Sarcoma Family of Tumors (ESFT) is the second most common malignant bone tumor of childhood (1, 2). In the past 25 years since the advent of 5-drug ESFT therapy, there has been very little improvement in overall patient survival particularly for patients with high risk metastatic or relapsed disease (1). Therefore, there exists a great need for agents that target the genes this tumor depends on for survival.

All ESFT tumors have fusion oncogenic transcription factors generated by chromosomal translocations involving the EWS gene and one of the ETS (E26 transformation-specific) family of transcription factors (3, 4). These transcription factors are highly dysregulated and believed to be critical to the biology of these tumors mediating both malignant transformation and progression (5).

In 85% of cases, the fusion transcription factor is EWS-FLI1 usually generated by the t(11;22)(q24;q12) chromosomal translocation (4). This transcription factor contains the binding domain of FLI1 and the transactivating domain of EWS but loses most of the regulatory domains of both proteins (6). Therefore, this protein is constitutively active and alters the expression of more than 500 genes (7). The resulting genetic program is believed to drive malignant transformation and clearly plays a central role in mediating the oncogenic phenotype (8-10). Most notably, EWS-FLI1 has been shown to directly or indirectly mediate the evasion of apoptosis and senescence, drive proliferation and even participate in the regulation of genes involved in metastasis (11-15). In addition, multiple groups have shown that knockdown of EWS-FLI1 with antisense DNA, siRNA or dominant negative methods is incompatible with ESFT cellular survival (16). Therefore, recent preclinical efforts have been focused on developing a small molecule therapy targeting this transcription factor (17, 18). Unfortunately, previously identified small molecule inhibitors have failed to demonstrate clinical activity against ESFT (19).

We have recently completed a high throughput screen of more than 50,000 compounds to identify mithramycin as an inhibitor of EWS-FLI1. We have utilized a novel approach combining a luciferase based primary screen and a gene signature multiplex PCR secondary screen to identify compounds that block the activity of EWS-FLI1 (20). In the primary screen, we required compounds to suppress the expression of luciferase driven by the promoter of a well- characterized EWS-FLI1 downstream target, NR0B1 without changing the expression of a constitutively active CMV driven promoter or decreasing cell viability as measured by an XTT assay (Figure 1). By performing these three screens in parallel, we were able to control for non-specific cytotoxic agents and general transcription inhibitors. We subsequently required the compounds to reverse a gene signature of more than 10 downstream targets of EWS-FLI1 utilizing a novel multiplex PCR assay that we developed to sort and prioritize compounds for further validation.

The compound that most effectively suppressed EWS-FLI1 activity was mithramycin (20). We showed that mithramycin suppresses the mRNA expression of our gene signature of EWS-FLI1 targets as well as an independent published gene signature of 50 different EWS-FLI1 targets. In addition, the suppression of EWS-FLI1 downstream targets also occurs at the protein level and leads to the induction of apoptosis in ESFT cells. These effects translate into a significant reduction of growth of two different xenograft models of Ewing sarcoma with one xenograft virtually eliminated from the mouse with mithramycin treatment (20). Finally, we found evidence of activity of mithramycin in

patients with Ewing sarcoma. Five patients with advanced, widely metastatic Ewing sarcoma were treated with mithramycin in the 1960s and at least one durable complete response was reported (21). The findings in our screen combined with the preclinical and clinical activity of mithramycin detailed below provide the rationale for the proposed phase I/II trial of mithramycin in children

and young adults with refractory solid tumors and Ewing sarcoma and EWS-FLI1 fusion transcript.

1.2.2 Preclinical studies

Mithramycin effectively suppresses the activity of EWS-FLI1 both *in vitro* and *in vivo*. We have shown by multiplex PCR, quantitative real time PCR and microarray expression profiling that mithramycin reverses the induction of two independently generated gene signatures of downstream targets of EWS-FLI1 (20). In addition, we have demonstrated that mithramycin suppresses the protein expression of two well-characterized downstream targets of EWS-FLI1, ID2 and NR0B1 in two different ESFT cell lines *in vitro* at nanomolar concentrations (22-24). The timing of this suppression correlates well with the induction of apoptosis and translates to an IC₅₀ of 10-15 nM in a panel of ESFT cell lines.

Finally, we used a xenograft model to show suppression of growth of two different ESFT xenografts. The TC32 xenograft model showed a regression of tumor in the first week of treatment that persisted long after every mouse in the control had to be sacrificed for progression. The TC71 xenograft also showed an impressive suppression in growth that translated into a doubling in survival for the affected mice. In contrast, despite relatively similar *in vitro* IC₅₀s, an osteosarcoma MNNG-HOS xenograft showed minimal suppression in growth and no improvement in survival with mithramycin treatment. In addition, we were able to recapitulate the biochemistry observed *in vitro* by utilizing immunohistochemistry to demonstrate suppression of NR0B1, an EWS-FLI1 downstream target, in the mithramycin treated but not the control tumor tissue (20).

In summary, ESFT depends on the continued expression of EWS-FLI1 for cell survival. We have completed a high throughput screen to identify mithramycin as an inhibitor of EWS-FLI1 and shown suppression of activity both *in vitro* and *in vivo*. As predicted, blockade of EWS-FLI1 causes the induction of apoptosis, leads to a nM *in vitro* IC₅₀ and suppresses growth of ESFT xenografts.

